Use of Sympatomimetic agents; n (%)	73 (1.1%)	70 (1.0%)	0.01	170 (1.1%)	183 (1.2%)	-0.01	0,243 (1.1%)	253 (1.2%)	-0.01
Use of CNS stimulants; n (%)	32 (0.5%)	29 (0.4%)	0.01	83 (0.5%)	76 (0.5%)	0.00	0,115 (0.5%)	105 (0.5%)	0.00
Use of estrogens, progestins, androgens; n (%)	274 (4.0%)	261 (3.8%)	0.01	634 (4.2%)	643 (4.3%)	0.00	0,908 (4.1%)	904 (4.1%)	0.00
Use of Angiogenesis inhibitors; n (%)	2 (0.0%)	0 (0.0%)	#DIV/0!	15 (0.1%)	2 (0.0%)	0.04	0,017 (0.1%)	2 (0.0%)	0.04
Use of Oral Immunosuppressants; n (%)	4 (0.1%)	6 (0.1%)	0.00	38 (0.3%)	29 (0.2%)	0.02	0,042 (0.2%)	35 (0.2%)	0.00
Use of fondaparinux or Bivalirudin; n	0 (0.0%)	3 (0.0%)	#DIV/0!	7 (0.0%)	2 (0.0%)	#DIV/0!	0,007 (0.0%)	5 (0.0%)	#DIV/0!
(%)									
Use of other direct thrombin inhibitors	0 (0.0%)	0 (0.0%)	#DIV/0!	0 (0.0%)	0 (0.0%)	#DIV/0!	0,000 (0.0%)	0 (0.0%)	#DIV/0!
(lepirudin, desirudin, argatroban); n (%)									
Use of Prasugrel ON CED; n (%)	90 (1.3%)	82 (1.2%)	0.01	104 (0.7%)	122 (0.8%)	-0.01	0,194 (0.9%)	204 (0.9%)	0.00
Use of Prasugrel 180 to 1 day prior; n	94 (1.4%)	90 (1.3%)	0.01	112 (0.7%)	134 (0.9%)	-0.02	0,206 (0.9%)	224 (1.0%)	-0.01
(%)									
Duration of index hospitalization (i.e. anchor hospitalization LOS)									

Table 1: Prasugrel 10 mg vs Clopidogrel 75 mg

mean (sd)	3.38 (1.65)	3.38 (1.50)	0.00	3.39 (1.39)	3.38 (1.34)	0.01	3.39 (1.48)	3.38 (1.39)	0.01
median [IQR]	3.00 [3.00, 4.00]	3.00 [3.00, 4.00]	0.00	3.00 [3.00, 4.00]	3.00 [3.00, 4.00]	0.00	3.00 (1.48)	3.00 (1.39)	0.00
Number of D-dimer tests									
mean (sd)	0.02 (0.17)	0.02 (0.17)	0.00	0.06 (0.26)	0.06 (0.26)	0.00	0.05 (0.24)	0.05 (0.24)	0.00
median [IQR]	0.00 [0.00, 0.00]	0.00 [0.00, 0.00]	0.00	0.00 [0.00, 0.00]	0.00 [0.00, 0.00]	0.00	0.00 (0.24)	0.00 (0.24)	0.00
Numbe of CRP, high-sensitivity CRP									
tests									
mean (sd)	0.04 (0.23)	0.04 (0.24)	0.00	0.04 (0.25)	0.04 (0.28)	0.00	0.04 (0.24)	0.04 (0.27)	0.00
median [IQR]	0.00 [0.00, 0.00]	0.00 [0.00, 0.00]	0.00	0.00 [0.00, 0.00]	0.00 [0.00, 0.00]	0.00	0.00 (0.24)	0.00 (0.27)	0.00
Number of PT or aPTTt tests									
mean (sd)	0.22 (1.04)	0.22 (0.99)	0.00	0.43 (0.98)	0.43 (1.00)	0.00	0.36 (1.00)	0.36 (1.00)	0.00
median [IQR]	0.00 [0.00, 0.00]	0.00 [0.00, 0.00]	0.00	0.00 [0.00, 0.00]	0.00 [0.00, 0.00]	0.00	0.00 (1.00)	0.00 (1.00)	0.00
Number of Bleeding time tests									
mean (sd)	0.00 (0.01)	0.00 (0.01)	0.00	0.00 (0.00)	0.00 (0.01)	0.00	0.00 (0.01)	0.00 (0.01)	0.00
median [IQR]	0.00 [0.00, 0.00]	0.00 [0.00, 0.00]	0.00	0.00 [0.00, 0.00]	0.00 [0.00, 0.00]	0.00	0.00 (0.01)	0.00 (0.01)	0.00
HAS-BLED Score (ICD-9 and ICD-10),									
180 days									
mean (sd)	3.41 (0.67)	3.42 (0.67)	-0.01	3.16 (0.49)	3.16 (0.50)	0.00	3.24 (0.55)	3.24 (0.56)	0.00
median [IQR]	3.00 [3.00, 4.00]	3.00 [3.00, 4.00]	0.00	3.00 [3.00, 3.00]	3.00 [3.00, 3.00]	0.00	3.00 (0.55)	3.00 (0.56)	0.00
Drug eluting stent; n (%)	3,921 (57.4%)	3,947 (57.7%)	-0.01	7,223 (47.8%)	7,159 (47.4%)	0.01	11,144 (50.8%)	11106 (50.6%)	0.00
Bare metal stent; n (%)	4,286 (62.7%)	4,285 (62.7%)	0.00	7,177 (47.5%)	7,200 (47.7%)	0.00	11,463 (52.3%)	11485 (52.4%)	0.00
Use of CYP inhibitors; n (%)	1,028 (15.0%)	1,027 (15.0%)	0.00	2,162 (14.3%)	2,184 (14.5%)	-0.01	3,190 (14.5%)	3211 (14.6%)	0.00
Use of CYP inducers; n (%)	27 (0.4%)	32 (0.5%)	-0.01	94 (0.6%)	83 (0.5%)	0.01	0,121 (0.6%)	115 (0.5%)	0.01
Commercial vs Medicare Advantage-									
Business Type Code - CORRECT ONE -									
TRUVEN									
Commercial; n (%)	4,740 (69.3%)	4,686 (68.6%)	0.02	2,090 (13.8%)	2,184 (14.5%)	-0.02	6,830 (31.1%)	6870 (31.3%)	0.00
Medicare Advantage; n (%)	2,095 (30.7%)	2,149 (31.4%)	-0.02	13,007 (86.2%)	12,913 (85.5%)	0.02	15,102 (68.9%)	15062 (68.7%)	0.00
Commercial vs Medicare Advantage-									
Business Type Code									
COM = COMMERCIAL; n (%)	4,740 (69.3%)	4,686 (68.6%)	0.02	-	-	#VALUE!	4,740 (69.3%)	4,686 (68.6%)	0.02
MCR = MEDICARE; n (%)	2,095 (30.7%)	2,149 (31.4%)	-0.02	-	-	#VALUE!	2,095 (30.7%)	2,149 (31.4%)	-0.02
MCD = MEDICAID; n (%)	0 (0.0%)	0 (0.0%)	#DIV/0!	-	-	#VALUE!	0 (0.0%)	0 (0.0%)	#DIV/0!
NONE = NO BUSINESS LINE CODE	0 (0.0%)	0 (0.0%)	#DIV/0!	-	-	#VALUE!	0 (0.0%)	0 (0.0%)	#DIV/0!
(added in 2015); n (%)									
UNK = UNKNOWN (added in 2015); n	0 (0.0%)	0 (0.0%)	#DIV/0!	-	-	#VALUE!	0 (0.0%)	0 (0.0%)	#DIV/0!
(%)									
Commercial vs Medicare Advantage-									
Data Type									
1 - Fee For Service; n (%)	-	-	#VALUE!	11,534 (76.4%)	11,465 (75.9%)	0.01	11,534 (76.4%)	11,465 (75.9%)	0.01
2 - Encounter; n (%)	-	-	#VALUE!	1,473 (9.8%)	1,448 (9.6%)	0.01	1,473 (9.8%)	1,448 (9.6%)	0.01
3 - Medicare; n (%)	-	-	#VALUE!	1,821 (12.1%)	1,920 (12.7%)	-0.02	1,821 (12.1%)	1,920 (12.7%)	-0.02
4 - Medicare Encounter; n (%)	-	-	#VALUE!	269 (1.8%)	264 (1.7%)	0.01	269 (1.8%)	264 (1.7%)	0.01
Metropolitan Statistical Area - Urban									
(any MSA) vs Rural (non-MSA)									
Urban; n (%)	-	-	#VALUE!	11,804 (78.2%)	11,827 (78.3%)	0.00	11,804 (78.2%)	11,827 (78.3%)	0.00
Rural; n (%)	-	-	#VALUE!	260 (1.7%)	269 (1.8%)	-0.01	260 (1.7%)	269 (1.8%)	-0.01
Unknown/Missing; n (%)	-	-	#VALUE!	3,033 (20.1%)	3,001 (19.9%)	0.01	3,033 (20.1%)	3,001 (19.9%)	0.01

Table 1: Prasugrel 10 mg vs Clopidogrel 75 mg

N of Generic name drugs									
mean (sd)	11.18 (9.42)	11.14 (10.51)	0.00	9.48 (7.70)	9.50 (8.54)	-0.00246	10.01 (8.27)	10.01 (9.20)	0.00
median [IQR]	8.00 [5.00, 15.00]	8.00 [4.00, 15.00]	0.00	7.00 [4.00, 12.00]	7.00 [4.00, 12.00]	0	7.31 (8.27)	7.31 (9.20)	0.00
N of Brand name drugs									
mean (sd)	3.70 (5.32)	3.73 (4.20)	-0.01	3.86 (4.85)	3.93 (3.99)	-0.02	3.81 (5.00)	3.87 (4.06)	0.05
median [IQR]	2.00 [1.00, 5.00]	2.00 [1.00, 5.00]	0.00	2.00 [1.00, 5.00]	2.00 [2.00, 5.00]	0	2.00 (5.00)	2.00 (4.06)	0.05

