5.3 Flowchart of the study cohort assembly

	Optum		Mar	ketScan
	Less Excluded Patients	Remaining Patients	Less Excluded Patients	Remaining Patients
All patients		75,524,500		191,990,035
Patients meeting the cohort entry criteria of moderate to high risk Acute Coronary Syndrome undergoing PCI procedure	-75219388	305,112	-191556394	433,641
Patients with sufficient enrollment period in the claims database	-41910	263,202	-120017	313,624
Patients with moderate to high risk Acute Coronary Syndrome	-144114	119,088	-165792	147,832
Patients initiating clopidogrel 75mg or prasugrel 10mg within 14 days of discharge of PCI hospitalization	-56497	62,591	-54511	93,321

Patients without history of hemorrhagic stroke	-349	62,242	-392	92,929
Patients without intracranial neoplasm, AV malformation, or aneurysm	-186	62,056	-202	92,727
Patients without ischemic stroke occurring 90 days prior to PCI hospitalization	-163	61,893	-255	92,472
Patients with sufficient claims enrollment after PCI hospital discharge	-483	61,410	-1191	91,281
Parent: Final cohort		61,410		91,281
Did not meet cohort entry criteria	-80	61,330	0	91,281
Excluded due to insufficient enrollment	0	61,330	0	91,281
Patients with no prior use of clopidogrel	-3135	58,195	-3653	87,628
Patients with no prior use of prasugrel	-535	57,660	-958	86,670
Patients without qualification in >1 exposure category	-18	57,642	-20	86,650
Patients age 18 years or older	-2	57,640	0	86,650
Patients without cardiogenic shock during PCI hospitalization	-1811	55,829	-2457	84,193
Patients without refractory ventricular arrhythmias	-5341	50,488	-7235	76,958
Patients without New York Heart Association Class IV congestive heart failure	-416	50,072	-265	76,693
Patients without active internal bleeding or history of bleeding diathesis	-3974	46,098	-3739	72,954
Patients without thrombocytopenia (platelet count of less than 100,000/mm3)	0	46,098	0	72,954
Patients without anemia (hemoglobin <10 g/DI)	-886	45,212	-2039	70,915
Patients without a claim for thienopyridine 5 days or less before PCI hospitalization	-1	45,211	-1	70,914
Patients without daily treatments with NSAIDs or COX-2 inhibitors	-394	44,817	-654	70,260
Patients without concomitant medical illness that is potentially associated with reduced survival	-687	44,130	-235	70,025
Patients without severe hepatic dysfunction	-1755	42,375	-2041	67,984
Patients without issues on poor treatment compliance including alcoholism, mental illness, or drug dependence	-2927	39,448	-1981	66,003

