Final cohort		39,448		66,003

6. Variables

6.1 Exposure-related variables:

Study drug:

The study exposure of interest is initiation of Prasugrel. Initiation will be defined by no use of Prasugrel or a comparator in the prior 6 months before treatment initiation (washout period).

Effectiveness research with Real World Data to support FDA's regulatory decision making: Protocol Template

Comparator agents:

- Initiators of prasugrel 10mg will be compared to initiators of-
 - Clopidogrel 75mg

6.2 Preliminary covariates:

- Age
- Sex
- Combined Comorbidity Index (CCI), measured over the default baseline covariate assessment period, defined as 180 days prior to and including index date

Covariates listed above represent only a small subset of covariates that will ultimately be controlled for in the design and analysis. We use the covariates above only for initial feasibility analyses to judge whether there is likely to be sufficient overlap between treatment groups to proceed with the study. Remaining covariates are defined only after the study has passed the initial feasibility analysis and the initial power assessment and are listed in Table 1 (Appendix B).

6.3 Outcome variables and study follow-up:

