6.3.1 Outcome variables

Effectiveness outcomes of interest (definitions provided in **Appendix A**):

- Primary outcome: 3-point major adverse cardiovascular events (MACE), i.e., non-fatal myocardial infarction, non-fatal stroke, or CV mortality
- Secondary outcomes: Individual components:
 - o Hospital admission for MI (for purposes of this individual component, fatal MI is included)
 - Hospital admission for stroke (for purposes of this individual component, fatal stroke is included)
 - All-cause mortality/CV mortality:
 - All-cause inpatient mortality identified using discharge status codes will be used as a proxy for "CV mortality" in Marketscan
 - In Optum, all-cause inpatient mortality + all-cause mortality for Medicare Advantage patients is used

Control outcome of interest (control outcome only serve to assess aspects of study validity but are not further interpreted):

- 1. Major bleeding (we expect to see increased risk with prasugrel; Wiviott, 2007)
- 2. Pneumonia (we expect to see a null association)

Control outcome definition

Outcome	Definition	Comments
Control Outcomes		
Major bleeding	Any inpatient diagnosis of major bleeding code list provided in Appendix A	Same code list used for both outcome and major bleed exclusion criteria

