Marketscan: https://bwh-dope.aetion.com/projects/details/990/results/46158/result/0

Date conducted: December 15, 2019

In order to complete the initial power analysis, the dummy outcome of a 90-day gap in database enrollment will be used. This outcome is used to ensure that no information on the comparative risks of the outcomes of interest are available at this stage. Complete a 1:1 PS-matched comparative analysis using this outcome. PS should include only 3 covariates: age, sex, and combined comorbidity index. Power calculations are based on the formulas from Chow et al. (2008).

In order to complete the initial power analysis, the dummy outcome of a 90-day gap in database enrollment will be used. This outcome is used to ensure that no information on the comparative risks of the outcomes of interest are available at this stage.

Effectiveness research with Real World Data to support FDA's regulatory decision making: Protocol Template

Complete a 1:1 PS-matched comparative analysis using this outcome. PS should include only 3 covariates: age, sex, and combined comorbidity index. Power calculations are based on the formulas from Chow et al. (2008).

Reviewed by PI:	[name]	Date reviewed:	12/16/19
Reviewed by FDA:	[name]	Date reviewed:	1/2/20
Reasons for stopping			
analysis (if required):			

9. Balance Assessment after PS matching

Aetion report links (Prasugrel vs. clopidogrel):

Optum: https://bwh-dope.aetion.com/projects/details/989/results/46940/result/0
Marketscan: https://bwh-dope.aetion.com/projects/details/990/results/46941/result/0

Date conducted: 01/05/2020

After review of initial feasibility and power analyses, complete creation of the remaining covariates (see Table 1 below for list of covariates). Again, using the dummy outcome of a 90-day gap in database enrollment, complete a 1:1 PS-matched analysis. The PS should include the complete list of covariates (excluding laboratory values, which are missing in some patients).

• Provide plot of PS distributions stratified by treatment group.

Note- Please refer to Appendix B.

Report covariate balance after matching.

Note- For Table 1, please refer to Appendix B.

• Report reasons for censoring by treatment group.

  		
Overall	Referent	Exposure

Effectiveness research with Real World Data to support FDA's regulatory decision making

Dummy Outcome	0 (0.00%)	0 (0.00%)	0 (0.00%)
Death	123 (0.28%)	70 (0.32%)	53 (0.24%)

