4	Fibrin-specific fibrinolytic therapy less than 24 h before randomization	N/A	
5	Non-fibrin-specific fibrinolytic therapy less than 48 h before randomization	N/A	
6	Active internal bleeding or history of bleeding diathesis	Measured 180 days prior to drug initiation in any diagnosis position and inpetient or outputient setting For active internal bleading, refer to the sheet "Bleading"	Cunningham A, Stein CM, Chung CP, Daugherty JR, Smalley WE, Ray WA. An automated database case definition for serious bleeding related to oral anticoagulant use. Pharmacoepidemiol Drug Saf. 2011;20(6):560–566. doi:10.1002/pds.2109
7	Clinical findings, in the Judgment of the investigator, associated with an increased risk of bleeding	or Bleeding distribusis: ICD-9: 286.x Coagulation defects 287.x Purpura and other hemorrhagic conditions	Huybrechts KF, Gopalakrishnan C, Bartels DB, Zint K, Gurusamy VK, Landon J, et al. Safety and effectiveness of debigatran and other direct oral anticoagulants compared to warfarin in patients with atrial fibrillation. Clin Pharmacol Ther. 2019 Dec 23.
	Any of the following:		
	a) History of hemorrhagic stroke	Measured any time prior to index hospitalization in any diagnosis position, inpatient or outpatient setting Hemorrhagic stroke: ICD-9: 430.xx, 431.xx ICD-10: ICD.xx, IS1.xx,	2018;360:k119 http://dx.doi.org/10.1136/bmj.k119 Patorno, Elisabetta et al. "Empagliflozin and the Risk of Heart Failure Hospitalization In Routine Clinical Care: A First Analysis from the Empagliflozin Comparative Effectiveness and Safety (EMPRES) Study." Circulation. 2019 Apr 8. doi:
		Measured 180 days prior to drug initiation in any diagnosis position and inpatient or	10.1161/CIRCULATIONAHA.118.039177
8	b) Intracranial neoplasm, arteriovenous malformation, or aneurysm	outpatient setting Intracrantal reopiasm ICD-9: 191.x, 225.0, 225.2, 225.4 ICD-10: C71.x, D32.x, D33.x, AV matformation (of brain) ICD-9: 747.81 ICD-10: Q82.x Corobra Aneuryem ICD-9: 437.3 ICD-10: 167.1	
	c) Ischemic stroke within 3 months prior to screening	Measured 90 days prior to Index hospitalization in any position, inpatient setting, isohemic stroke:	Patorno, Elisabetta et al. "Cardiovascular outcomes associated with canagliflozin versus other non-giflozin antidiabetic drugs: population based cohort study," BMJ 2018;360:k19 http://dx.doi.org/10.1136/bmj.k119 Patorno, Elisabetta et al. "Empgliflozin and the Risk of Heart Failure Hospitalization

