		ICD-9: 433.xx, 434.xx, 436.xx ICD-10: I63.xx I65.xx I66.xx	in Routine Clinical Care: A First Analysis from the Empagliflozin Comparative Effectiveness and Safety (EMPRISE) Study." Circulation. 2019 Apr 8. doi: 10.1161/CIRCULATIONAHA.118.039177
9	International normalized ratio known to be greater than 1.5 at the time of screening	N/A	
10	Platelet count of less than 100000/mm3 at the time of screening	Measured during index hospitalization in inpatient setting, any position Thrombosytopenia: ICD-10: D99, Bobd-4x, D69.5x, D69.2x, D69.3x ICD-9: 287.3x, 287.4x	
11	Anemia (hemoglobin b10 g /dL) at the time of screening	Meesured during Index hospitalization in Inpetient setting, any position ICD-9: 280.0 Iron deficiency anemia secondary to blood loss (chronic) 285.1 Acute most hemorrhaeic anemia! 285.9 (Anemia unspecified)	
11	Anemia (hemoglobin b $10\mathrm{g/dL}$) at the time of screening		

	Prior/concomitant therapy exclusion criteria		
12	One or more doses of a thienopyridine 5 d or less before PCI	Prescription for following drugs 5 days prior to Index hospitalization Clopidogrel, prasugrel, or ticlopidine	
13	Oral anticoagulation or other antiplatelet therapy that cannot be safely discontinued for the duration of the study	N/A	
	Daily treatment with nonsteroidal antiinflammatory drugs (NSAIDs) or cyclooxygenase-2 inhibitors (COX-2 inhibitors)	More than 150 days of supply out of 180 days prior to drug initiation NSAID: aspirin, ibuprofen, naproxen >> OTC cannot be captured COX-2 inhibitors: celecoxib	
	General exclusion criteria		
15		N/A	
16	Employed by Eli Lilly and Company; Ube Industries Limited, Dalichi Sankyo Co.; The TIMI Study Group; Quintiles	N/A	
17	Treatment within the last 30 d with an investigational drug or are presently enrolled in another drug or device study	N/A	
18	Previously completed or withdrawn from this study or any other study investigating prasugrel	N/A	
19	Women who are known to be pregnant, have given birth within the past 90 d, or are breast-feeding	N/A	
20		Following Index score measured 180 days prior to drug Initiation Combined comorbidity index CCI >=10	Gagne, Josh J et. al. "'A combined comorbidity score predicted mortality in elderly patients better than existing scores." J Clin Epidemiol. 2011 Jul;64(7):749-59. doi: 10.1016/j.jclinepi.2010.10.004. Sun, Jenny W et. al. "Validation of the Combined Comorbidity Index of Charlson and Elixhauser to Predict 30-Day Mortality Across ICD-9 and ICD-10." Med Care. 2018

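### Apart from intracranial neoplasm, cancer reaches the exclusions and the propensity score only through composite scores, while all-cause death stands in for CV death

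*Combined protocol and SAP*

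**What the plan says.** **Exclusion.** The Section 5.3 flowchart has the step "Patients without concomitant medical illness that is potentially associated with reduced survival", which removes 687 patients in Optum and 235 in MarketScan. Appendix A, exclusion 20, defines it by one rule: "Following Index score measured 180 days prior to drug Initiation Combined comorbidity index CCI >=10". The only exclusion shown that names a neoplasm is 8b, "Intracranial neoplasm, arteriovenous malformation, or aneurysm".

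**Covariates.** Section 6.2 names "Combined Comorbidity Index (CCI), measured over the default baseline covariate assessment period" as a preliminary covariate and says that the remaining covariates "are listed in Table 1 (Appendix B". Section 9 sets the PS content: "The PS should include the complete list of covariates (excluding laboratory values, which are missing in some patients". Table 1 has rows for cancer screening (mammogram, PSA, Pap smear, fecal occult blood) but none for cancer itself. Its only row with the word malignant is malignant hypertension.

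**Outcome.** Section 6.3.1 makes CV death part of the primary composite. For MarketScan it states: "All-cause inpatient mortality identified using discharge status codes will be used as a proxy for" CV mortality. For Optum it uses all-cause inpatient death plus all-cause death in Medicare Advantage members. Appendix A mentions cause of death only for Medicare, through a later linkage, and Medicare is not one of the two data sources in Section 3.

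**The concern.** Active cancer can raise the risk of death, and it may influence the choice of antiplatelet drug. If it is commoner among the matched clopidogrel patients, the referent event rate is too high and the MACE HR is too low. That is the direction of the trial result of 0.81, so the bias would look like successful replication and would not prompt suspicion.

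Table 1 makes this direction plausible, though it does not prove it. Before matching, clopidogrel patients are older (mean 62.76 vs 56.98) and have higher CCI (2.32 vs 1.79) and HAS-BLED (3.52 vs 3.24). After matching, the group aged 75 or over is still larger on clopidogrel.

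A balanced composite does not settle the matter, because two arms can share a mean score while differing in what makes it up.

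**Working it through.** **1. Reach of the exclusion.** Patients reaching the step (Section 5.3): 44,817 + 70,260 = 115,077. Removed: 687 + 235 = 922, or 922/115,077 = 0.8%. Among clopidogrel patients left before matching, mean CCI is 2.89 (SD 2.14) in Optum and 1.95 (SD 1.72) in MarketScan, so a cut at 10 lies far in the tail.

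**2. Can a summary balance while its parts do not?** Table 1 contains an example. Matched mean age is 56.82 vs 57.02 (printed standardised difference -0.02), yet age 75 or over is 1,444 vs 681 (0.16). Matched CCI of 1.78 vs 1.79 therefore cannot establish that cancer is balanced.

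**3. Events and deaths.** Section 10 event counts reproduce as 2 × n × risk/1,000:
- Optum: 2 × 6,835 × 58.63/1,000 = 801.47
- MarketScan: 2 × 15,097 × 45.09/1,000 = 1,361.45
- Sum: 2,162.92

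The plan's pooled 2,274.79 uses 51.86 per 1,000, the unweighted mean of the two risks. The Section 9 censoring table lists 123 deaths (70 referent, 53 exposed). Share of events: 123/2,162.92 = 5.7% (5.4% on 2,274.79). The two counts come from different runs, so this share is approximate.

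**4. Size of the possible bias.** Let p0 and p1 be cancer prevalence on clopidogrel and prasugrel, and RR the relative risk. The documents give none of these; all are assumed.
- Whole composite: factor = (1 + p1(RR−1)) / (1 + p0(RR−1))
- Deaths only, with s = 0.0569: factor = (1 + s·p1(RR−1)) / (1 + s·p0(RR−1))

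| p0 | p1 | RR | Whole composite | Deaths only |
|---|---|---|---|---|
| 2% | 1.5% | 1.5 | 1.0075/1.010 = 0.998 | 1.000 |
| 3% | 1.5% | 2 | 1.015/1.030 = 0.985 | 0.999 |
| 4% | 1% | 2 | 1.010/1.040 = 0.971 | 0.998 |
| 4% | 1% | 3 | 1.020/1.080 = 0.944 | 0.997 |

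At the far corner a true HR of 0.81/0.944 = 0.86 would read as 0.81. A much harsher set (8% vs 4%, RR 5) gives 1.16/1.32 = 0.88 on the whole composite and 0.991 through deaths only.

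**5. The angiogenesis-inhibitor row.** The pooled counts in "Use of Angiogenesis inhibitors; n" (%) reproduce from the two databases.
- Before matching: 14 + 29 = 43 of 83,351 vs 0 + 2 = 2 of 22,059. Ratio 5.7, standardised difference 0.024.
- After matching: 2 + 15 = 17 vs 0 + 2 = 2, each of 21,932. Ratio 8.5, Fisher p = 0.0007 uncorrected.

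From exact matched counts the standardised difference is (0.000775 − 0.000091)/√((0.000775 + 0.000091)/2) = 0.033. The printed 0.04 comes from the rounded 0.1% and 0.0% (0.0447). If all 15 excess users had one extra event each, a ratio of 1.00 would become 1,081.5/(1,081.5 + 15) = 0.986.

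**The case against.** **Cancer is partly handled.** This stands. Exclusion 8b removes intracranial neoplasm, CCI of 10 or more may remove some cancer patients, and CCI and the frailty score are Table 1 rows that match closely. The documents do not list the components of CCI, so the share of cancer already absorbed cannot be judged in either direction. Appendix A also refers readers to an external folder for missing detail, so statements about exclusions apply to the appendix as shown.

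**The angiogenesis-inhibitor row.** A reader might infer from 17 vs 2 that an imbalance in cancer survived the match. The documents do not support that. Under the Section 9 rule this row is itself a PS covariate, so its residual gap cannot show what omitting a covariate does. It covers 19 of 43,864 patients, was picked out from many rows, and lies well below the commonly used 0.1. The documents give no drug list or indication, so its link to cancer is assumed. It is at most a weak hint.

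**The magnitude is assumed.** This also stands. The 0.944 end needs a four-fold difference in prevalence to survive matching and a three-fold risk of MI and stroke as well as death. Through the death proxy alone the effect is below 1%.

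**Other safeguards.** Bleeding and anemia exclusions apply, HAS-BLED matches at 3.24 vs 3.24, and pneumonia is a planned null control. These help, but none is specific to cancer, and the plan does not say how large an imbalance the pneumonia control could detect.

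**Conclusion.** The gap is real but modest. In the documents as shown, cancer other than intracranial neoplasm is neither a named exclusion nor a named covariate, and adjustment through composites is of unknown extent. This rests on the covariate list and Appendix A alone; it does not need the angiogenesis-inhibitor row.

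Under the assumed 2-4% vs 1-1.5% prevalence and RR of 1.5-3, the HR is multiplied by 0.944-0.998 if cancer raises the whole composite, and by more than 0.99 if it acts only through deaths. The likely effect is small. The direction, lower HR, further assumes that residual cancer is commoner on clopidogrel.

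Two stronger readings are not supported. One is that cancer is wholly ignored: 8b and the CCI rule contradict it. The other is that cancer alone could turn a null result into 0.81: even the harshest scenario above reaches only 0.88. A cheap improvement is warranted; nothing here invalidates the design.

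**What to change.** Add two baseline indicators from diagnosis claims over the 180-day window, to both the Section 9 PS and Table 1: active malignancy (excluding non-melanoma skin cancer) and metastatic disease. Re-run the 1:1 match in each database and report both indicators before and after matching, ahead of the Section 13 analyses. Section 9 uses a dummy outcome and Section 13 has no date conducted, so this can be done without sight of comparative results.

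The cost is two code lists, a re-run of the match and a few changed pairs; no new data are needed. If the indicators prove balanced, the question is closed with evidence.

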5.2.1 Eligible cohort entry dates

Market availability of prasugrel in the U.S. started on 2009-07-10.

- For Marketscan: 2009-07-10 to 2017-12-31 (end of data availability).
- For Optum: 2009-07-10 to 2019-03-31 (end of data availability).

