Start of an additional exposure	3,840 (8.75%)	580 (2.64%)	3,260 (14.86%)
End of index exposure	22,870 (52.14%)	11,391 (51.94%)	11,479 (52.34%)
Specified date reached	3,735 (8.51%)	2,262 (10.31%)	1,473 (6.72%)
End of patient enrollment	12,361 (28.18%)	7,033 (32.07%)	5,328 (24.29%)
Switch to ticagrelor (for censoring) + nursing home admission	935 (2.13%)	596 (2.72%)	339 (1.55%)

• Report follow-up time by treatment group.

Median Follow-Up Time (Days) [IQR]				
Patient Group Optum Marketscan				
Overall Patient Population	276 [98-453]	312 [122-481]		
Referent	332 [124-532]	344 [144-530]		
Exposure	222 [82-405]	281 [111-443]		

• Report overall risk of the primary outcome.

	Optum	Marketscan
Risk per 1,000 patients (MACE)	58.63	45.09

10. Final Power Assessment

Date conducted:

- Re-calculate power in the appropriate excel table, using the revised number of matched patients from the PS-match in Section 9. All other parameters in the table should be the same as in Section 8. If the study is to be implemented in more than one database, copy and paste excel sheet to report power for each database separately and for the pooled analysis that uses data from all databases together. Power calculations are based on the formulas from Chow et al. (2008).
 - Pooled
 - For prasugrel 10mg vs. clopidogrel 75mg (Primary outcome- MACE)

Superiority Analysis		Non-inferiority Analysis	
Number of patients matched		Number of patients matched	
Reference	21,932	Reference	21,932
Exposed	21,932	Exposed	21,932
Risk per 1,000 patients	51.86	Risk per 1,000 patients	51.86
Desired HR from RCT	0.8	Assumed HR from RCT	1
Alpha (2-sided)	0.05	Alpha (2-sided)	0.05
		Non-inferiority margin	1.3
Number of events expected	2274.78704	Number of events expected	2274.78704
Power	0.999612288	Power	0.999991333

o Optum

For prasugrel 10mg vs. clopidogrel 75mg (Primary outcome- MACE)

Superiority Analysis		Non-inferiority Analysis	
Number of patients matched		Number of patients matched	
Reference	6,835	Reference	6,835
Exposed	6,835	Exposed	6,835
Risk per 1,000 patients	58.63	Risk per 1,000 patients	58.63
Desired HR from RCT	0.8	Assumed HR from RCT	1
Alpha (2-sided)	0.05	Alpha (2-sided)	0.05
		Non-inferiority margin	1.3
Number of events expected	801.4721	Number of events expected	801.4721
Power	0.884670943	Power	0.960270972

MarketScan

For prasugrel 10mg vs. clopidogrel 75mg (Primary outcome- MACE)

Tot prasagret total vs. clopidogret 75 mg (1 milar y outcome-winee)			

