Generic Name	prasugrel
Sponsor	Eli Lilly
Year	2009
	Primary composite endpoint of death from
Measurable endpoint	cardiovascular causes, nonfatal myocardial
I Wicasarabic Chaponic	infarction, or nonfatal stroke. The key
	safety end point was major bleeding.
Exposure	Prasugrel
Comparator	Clopidogrel
	patients with moderate-to-high-risk acute
Population	coronary syndromes with scheduled
	percutaneous coronary intervention
Trial finding	HR = 0.81 (95% CI 0.73–0.90)
Notes	
No. of Patients	13,608
Non-inferiority margin	-
Assay Sens. Outcome	
Assay Sens. Endpoint (from trial)	
Finding for potential Assay Sens.	
Outcome from trial-	
Power	0.90 to detect 20% reduction in the relative
	risk
Blinding	Double-blinded

Statistical Method	
	for the prevention of thrombotic
Approval indication	cardiovascular complications in acute
	coronary syndromes

Mortality-Dependent on data source.

1. All-cause mortality / inpatient mortality Identified using the vital status file-

Medicare

Identified using the discharge status codes-

Optum-

- 20 = EXPIRED
- 21 = EXPIRED TO BE DEFINED AT STATE LEVEL
- 22 = EXPIRED TO BE DEFINED AT STATE LEVEL
- 23 = EXPIRED TO BE DEFINED AT STATE LEVEL
- 24 = EXPIRED TO BE DEFINED AT STATE LEVEL
- 25 = EXPIRED TO BE DEFINED AT STATE LEVEL
- 26 = EXPIRED TO BE DEFINED AT STATE LEVEL
- 27 = EXPIRED TO BE DEFINED AT STATE LEVEL
- 28 = EXPIRED TO BE DEFINED AT STATE LEVEL
- 29 = EXPIRED TO BE DEFINED AT STATE LEVEL
- 40 = EXPIRED AT HOME (HOSPICE)
- 41 = EXPIRED IN A MEDICAL FACILITY (HOSPICE)
- 42 = EXPIRED PLACE UNKNOWN (HOSPICE)

Truven-

- 20 Died
- 22 Died
- 23 Died
- 24 Died
- 25 Died
- 26 Died
- 27 Died
- 28 Died
- 29 Died
- 40 Other died status or Expired at home (Hospice claims only) (depends on year)
- 41 Other died status or Expired in medical facility (Hospice claims only) (depends on year)

- 42 Other died status or Expired place unknown (Hospice claims only) (depends on year)
- 21 Died or Disch./Transf. to court/law enforcement (depends on year)

2. CV mortality

Information on CV mortality through data linkage with the National Death Index (NDI) will be available for Medicare at a later date. We will conduct secondary analyses using CV mortality at that time.

Major bleeding co	Major bleeding control outcome: 1 inpatient (any position)		
Major bleeding exclusion criteria: 1 inpatient (any position) or 2 outpatient diagnosis (separated by 7-365 days)			

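### The MarketScan death list includes discharge status 21 with no year limit, although its own label gives a discharged-alive meaning in some years

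*Combined protocol and SAP*

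**What the plan says.** The mortality definition in Appendix A identifies all-cause and inpatient death by code lists, one per database, under the line "Identified using the discharge status codes". The last entry of the Truven list is "21 Died or Disch./Transf. to court/law enforcement (depends on year". Codes 40 to 42 on that list also vary by year; the first of them reads "40 Other died status or Expired at home (Hospice claims only) (depends on year".

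Section 6.3.1 makes the primary outcome "3-point major adverse cardiovascular events (MACE), i.e., non-fatal myocardial infarction, non-fatal stroke, or CV mortality". For MarketScan it adds: "All-cause inpatient mortality identified using discharge status codes will be used as a proxy for" cardiovascular mortality. The same deaths form the mortality outcome listed among the secondary components.

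Section 6.3.2 ends as-treated follow-up at a measured death. For the intention-to-treat analysis it replaces only the switching, augmentation and discontinuation rules, so death ends follow-up there too.

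Section 5.2.1 gives the entry window: "For Marketscan: 2009-07-10 to 2017-12-31 (end of data availability".

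**The concern.** A list that defines death should hold only codes that mean death in the data to which they are applied. Status 21 does not meet that test on its own label, and the plan states no rule for choosing between its two meanings.

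If the list is coded as printed, a patient discharged to court or law enforcement during follow-up is recorded as dead. One such record has three effects. It adds a false event to primary MACE, it adds a false event to the mortality outcome, and it cuts off real follow-up. Death is also the component with few events, so a given number of false records weighs more there than in the composite.

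**Working it through.** **1. Which database is affected.** The PS-matched Truven columns of Table 1 hold 15,097 patients per arm, as does the MarketScan power table in Section 10. Truven and MarketScan are the same source, so the point concerns MarketScan only.

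**2. The year-dependent codes side by side.**

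| Code | Database | Varies by year | A non-death meaning on the label |
|---|---|---|---|
| 40, 41, 42 | MarketScan | yes | no: both meanings are death |
| 21 | MarketScan | yes | yes: court or law enforcement |
| 21 | Optum | no | no: labelled as expired, in the same words as 22 to 29 |

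Only MarketScan 21 carries a meaning under which the patient is alive.

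**3. Whether a year rule is printed.** None appears in the mortality definition of Appendix A, in Section 6.3.1 or in Section 6.3.2. The eligible entry dates span more than eight calendar years.

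**4. The plan's own figures, reproduced.** Inputs from Section 10, MarketScan: 15,097 per arm, risk 45.09 per 1,000, HR 0.8, two-sided alpha 0.05.
- Expected events: 2 × 15,097 × 45.09 / 1,000 = 1,361.447 (stated: 1361.44746).
- Power: Φ(√1,361.447 × |ln 0.8| / 2 − 1.960) = Φ(36.898 × 0.11157 − 1.960) = Φ(2.157) = 0.9845 (stated: 0.984488939).

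**5. Size under assumed counts.** The documents give no count of status-21 records, so k false deaths is an assumption throughout. The share is k / 1,361.447. For the hazard ratio, take a true value of 0.80 and split the false deaths equally between arms. With T = 1,361.447 − k true events, the event ratio is approximately (0.8T/1.8 + k/2) / (T/1.8 + k/2). This is a simple illustration that ignores differences in follow-up between the arms.

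| k (assumed) | Share of MarketScan MACE | Observed ratio if kept | Power if kept | Power if removed |
|---|---|---|---|---|
| 5 | 0.37% | 0.8007 | 0.9839 | 0.9842 |
| 10 | 0.73% | 0.8013 | 0.9833 | 0.9839 |
| 25 | 1.84% | 0.8033 | 0.9813 | 0.9829 |
| 50 | 3.67% | 0.8066 | 0.9775 | 0.9813 |
| 123 | 9.03% | 0.8164 | 0.9626 | 0.9754 |

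The column for power if kept uses all 1,361.447 events at the diluted ratio. The column for power if removed uses T events at HR 0.8. The last row is an extreme bound that treats every death in the Section 9 censoring table as a MarketScan status-21 record.

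**6. What the death count can show.** The rows of that table sum to 123 + 3,840 + 22,870 + 3,735 + 12,361 + 935 = 43,864 = 2 × 21,932. The 123 deaths (70 referent, 53 exposed) are therefore pooled over both databases. They come from the dummy-outcome run and are not split by database. They show that recorded deaths are few, but they give no MarketScan denominator.

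**The case against.** The strongest reply is that the documents show an ambiguity, not an error in the data. The label itself says that the meaning varies by year, so the authors had seen the problem. Appendix A sends the reader to an external folder for missing details, and Section 2 says that the implementation steps are archived in the platform. A year filter may exist in either place. The documents also do not say which years carry the court meaning. If none fall in the study period, no false death arises.

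This reply stands in part. A reader might infer that the plan counts status 21 as death in every year, or that false deaths are known to be present. The documents support neither inference. They support only that no year restriction is stated and that the printed rule permits the error. The reply does not remove the point, because under Section 12 this document is the one to be registered, and its death definition should be complete on the page.

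Two other extensions are tempting. One is to apply the same check to Optum 21. Its label gives no year dependence and no living meaning, and it matches 22 to 29, so nothing singles it out. The other is to divide 5 to 10 records by the 123 deaths and report 4% to 8%. That sets an assumed MarketScan numerator against a pooled count, so it does not measure the affected component.

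It is also fair to say that the effect on the primary result is very small. Follow-up starts only after the post-discharge prescription fill, so only a later hospital stay could produce a false death. Nothing in the documents suggests a difference between arms.

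**Conclusion.** The point holds as a minor correction to the MarketScan death definition. As printed, it lets a code with a discharged-alive meaning count as death, with no year limit, in the primary composite, in the mortality outcome and in the end of follow-up.

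On the assumed 5 to 10 records, the share of expected MarketScan MACE events is 0.37% to 0.73%. A true ratio of 0.80 would then appear as about 0.801, and power would stay at about 0.98. The ratio and power figures also assume an equal split between arms. The effect on the primary hazard ratio and power is negligible. The relevance is mainly to the mortality component, where the size cannot be stated because no MarketScan death count is given. Whether any record is affected depends on the data dictionary, which is not part of the documents.

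**What to change.** In the Truven list of Appendix A, attach a year condition to status 21: it counts as death only in data years in which the MarketScan dictionary defines it as died, and it is dropped in all other years. Name those years in the list. If a filter is already built into the platform, one sentence saying so is enough. Leave the other MarketScan codes and the Optum list as they are.

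With the results, report how many MarketScan deaths and how many MACE events rest on status 21 alone. This replaces the assumed range above with a count.

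The cost is a dictionary check, one condition on one code, and a rerun of the MarketScan death definition. The date of the comparative analyses in Section 13 is blank, so on the face of the document the change can be made before any treatment effect is seen.
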